13.4 Expected Event of Special Interest

For SAE's that meet the criteria of Expected Adverse Events as detailed in the list below, completion of an SAE form is NOT required; however such events should be recorded on the appropriate CRF form as soon as possible.

For all Expected AEs details recorded on the CRF will include the onset date; whether or not it was an SAE; level of severity (from 1 mild to 3 severe); whether or not medication was required (yes/no) and the AE outcome (unknown, ongoing, resolved, and if resolved the date of resolution).

The data centre will subsequently generate SAE and AE reports for review by the TSC.

A list of expected adverse events in relation to the intervention and/or study participation (i.e. outcome assessment) is provided below:

- Transient post exercise soreness
- Post exercise stiffness
- Post-exercise fatigue
- Temporary exacerbation of disease-related inflammatory pain during exercises
- Trips, slips and/or falls during set-up of circuit, during exercises, and/or clearing away the circuit setup
- Temporary musculoskeletal pain from set-up of circuit at home
- Perceptions of new instance of disease flare resulting from undertaking gait rehabilitation circuit.

14. Intervention

There is strong evidence from the field of neurological rehabilitation suggesting that repetitive practice of walking tasks results in improvements in walking ability by improving lower limb function [50,90-92]. Preliminary evidence suggests that similar interventions are beneficial for improving walking ability in RA [51,52]. Our gait rehabilitation intervention is a complex intervention which can be described as individually tailored and progressed, which is to be supervised in clinic and practiced at home. It will consist of 3 main components in addition to usual care: -

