To monitor safety arising as a result of the intervention, serious adverse events (SAEs), and expected events will be recorded. The physiotherapists or podiatrists delivering the intervention will record SAEs during each intervention session, using a SAE reporting form according to the Glasgow CTU standard operating procedures for RCTs. Participants and the local personnel (intervention clinicians and outcome assessors) may report SAEs to the study team at any time. In addition, at the end of the intervention period the independent outcomes assessor will ask participants whether or not they have experienced SAEs over the 12-weeks intervention period. Expected events (defined as specific non-serious events that might be related to the intervention) will be monitored and recorded using a standard form as part of the case report form (CRF). These will be evaluated by the trial management group (TMG) to determine these are related to the intervention or study and will therefore be recorded as adverse events. Adverse events will then be reported to the trial steering committee (TSC). Given the study population, expected harms might include falling, fatigue, pain and post-exercise muscle soreness (see section 5. Assessment of Safety).

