13.3 Recording and Reporting AEs/SAEs

Participants will be asked at clinical visits whether or not they have experienced any adverse effects from the study intervention or study procedures. All AEs will be recorded in participant's clinical notes.

- AEs and SAEs occurring before enrollment will not be recorded or reported.
- Participants will be asked at each study visit about the occurrence of any AEs.
- All SAEs occurring within the 12 weeks of the intervention will be recorded.
- All AEs must be assessed for seriousness. SAEs must be assessed for causality, expectedness and severity.
- An SAE occurring to a research participant must be reported to the main Research Ethics Committee (REC) within 15 days of notification, where in the opinion of the Chief Investigator the event was:

"Related" that is, it resulted from administration of any of the research procedures And

"Unexpected" that is the type of event is not an expected occurrence as a result of the intervention provided.

Causality - This should be assessed by the CI or PI and should be described using the following categories:

- Unrelated to intervention
- Possibly related to intervention
- Probably related to intervention
- Definitely related to intervention

Severity - This should be assessed by the CI or PI and should be described using the following categories:

Mild:	awareness of event but easily tolerated
Moderate:	discomfort enough to cause some interference with usual activity
Severe:	inability to carry out usual activity

Details of SAE's arising during the trial should be entered in to the Non-cTIMP SAE reporting form, provided to the research sites. The site must enter details in the form and submit to the sponsor contact provided within 24 hours of first becoming aware of the event and any follow Version Date: 11th Feb 2018 Version Number: 1.2

up information should also be reported. Such events must be reported to sponsor in order to capture all potential related adverse events.

SAE forms should be completed and sent with 24 hours of becoming aware to a member of the GREAT study team at Glasgow Caledonian University, using the designated SAE form for non-CTIMPs using the designated email inbox.

The paper SAE form should be completed and emailed to: [contact]

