For the purposes of evaluating measurement properties of primary outcome candidates, we have selected a minimum magnitude of association (correlation coefficient) between the selected anchor and outcome measures of r=0.65 [101,102]. With a feasibility study sample size of at least n=42, we can detect a correlation \geq 0.65 at 5% significance with 80% power, accounting for 20% attrition.

19. Management and delivery

The Robertson Centre for Biostatistics which is part of the Glasgow Clinical Trials Unit and a fully UKCRC-registered Clinical Trials Unit, will manage and analyse data. All statistical analyses will be conducted according to the pre-specified Statistical Analysis Plan.

20. Study closure / definition of end of study

The study will end when the TSC agrees that one or more of the following situations applies:

• Last participant, last study visit (including qualitative interviews);

OR

i. The planned sample size for each aspect of the study (repeated measures plus embedded qualitative work) has been achieved;

- ii. New information makes it inappropriate to continue to deliver the study intervention;
- iii. Recruitment is so poor that completion of the study cannot reasonably be anticipated.

21. Case report forms

A paper-based case report form (CRF) will be used to collect study data. The CRF will be developed by the study Data Centre at the Robertson Centre for Biostatistics, University of Glasgow. Site-specific personnel will complete the CRF for each participant and will subsequently securely mail completed CRFs to the Data Centre at the Robertson Centre for Biostatistics. Paper-based CRFs will be anonymised and will not include any identifiable information. Study personnel at the Data Centre will enter CRF data into an eCRF for analysis. Access to the eCRF will be restricted, with only authorised data centre personnel able to make entries or amendments to participants' data. It is the investigator's responsibility to ensure completion and to review and approve data captured in the CRF.

All data handling procedures will be detailed in a Study Specific Data Management Plan. Data will be validated at the point of entry into the eCRF and at regular intervals during the study. Data discrepancies will be flagged to the study site and any data changes will be recorded in order to maintain a complete audit trail (reason for change, date change made, who made change).

22. Record retention

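### Section 13.4 waives the SAE form for serious events of a listed type, contradicting 12.2 and 13.3 and taking a serious fall off the 24-hour route

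*Protocol*

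**What the plan says.** Four parts of the protocol bear on how a serious event of an expected type is reported.

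- **Section 12.2** introduces the class this way: "Expected events (defined as specific non-serious events that might be related to the intervention". It has these events recorded on a standard CRF form and reviewed for relatedness by the trial management group (TMG). It has therapists record SAEs on an SAE reporting form.
- **Section 13.2** makes an event serious if, among other criteria, it requires hospitalisation.
- **Section 13.3** states that "SAEs must be assessed for causality, expectedness and severity". SAE details go on the non-CTIMP SAE form, which is sent within 24 hours of awareness. The reason given is: "Such events must be reported to sponsor in order to capture all potential related adverse events". The chief investigator, with the local principal investigator, then uses that form to judge whether the event is related and whether it is expected.
- **Section 13.4** says that for SAEs "that meet the criteria of Expected Adverse Events as detailed in the list below, completion of an SAE form is NOT required", and continues: "however such events should be recorded on the appropriate CRF form as soon as possible". The details to be recorded "will include the onset date; whether or not it was an SAE; level of severity (from 1 mild to 3 severe"), and then "whether or not medication was required (yes/no) and the AE outcome". The list has seven items. One is trips, slips and falls while setting up, performing or clearing away the circuit.

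Section 21 says how the CRF travels: site personnel "will subsequently securely mail completed CRFs to the Data Centre".

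**The concern.** Section 13.4 takes the SAE form away from serious events whose type is on the list. The list names events expected in relation to the intervention or to study participation, so these are the serious events for which a link to the intervention is most plausible. The 24-hour limit and the investigators' judgement of relatedness both depend on that form, so waiving the form removes both.

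The exemption also conflicts with the rest of the protocol. If expected events are non-serious by definition, no SAE can be an expected event and the exempted class should be empty. If every SAE goes on the SAE form, there is no room for an exemption.

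Safety is a stated objective (sections 2.2.3 and 6). Section 13.1 says that the intervention has not been used in early RA, section 5.1 notes a raised risk of falls in RA, and section 14 has the circuit practised at home. Sites need a single answer on how to report a serious fall.

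**Working it through.** No arithmetic applies: the point depends on a reporting rule, not on a sample size, error rate or effect. The check is to follow one event through each section. The example is a fall during the exercises that leads to hospital admission.

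| Step | Section | Result for this event |
|---|---|---|
| Is it serious? | 13.2 | Yes, by the hospitalisation criterion |
| Is it an expected event? | 12.2 | No, because that class is defined as non-serious |
| Is it an expected event? | 13.4 | Yes, because falls during exercises are listed with no limit on seriousness |
| Is an SAE form needed? | 12.2, 13.3 | Yes; neither section states an exception |
| Is an SAE form needed? | 13.4 | No |
| Time limit | 13.3 | 24 hours from awareness, attached to the SAE form |
| Time limit | 13.4, 21 | No hour limit; prompt entry on a paper CRF, which is mailed |
| Causality assessment | 13.3 | Required for SAEs; relatedness and expectedness are judged from the SAE form |
| Causality assessment | 13.4 | Listed fields are onset date, SAE yes/no, severity, medication and outcome; none is for causality |

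Three things follow.

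1. A site cannot comply with 12.2, 13.3 and 13.4 together. Sections 12.2 and 13.4 disagree on whether the event is an expected event, and 13.3 and 13.4 disagree on whether the form is needed.
2. Section 13.4 waives the form but does not expressly waive the 13.3 duty to assess causality. The duty remains, but the form that carried it is gone and the listed CRF fields do not replace it.
3. The order of decisions changes. Under 13.3 the chief investigator, with the local investigator, decides expectedness from a completed SAE form. Under 13.4 the event has to be matched to the list before any SAE form exists.

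Next, what survives under 13.4:

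- The CRF records whether the event was an SAE, with its severity and outcome.
- The data centre produces SAE and AE reports for the TSC (13.4).
- The TMG reviews the relatedness of expected events (12.2), although that section describes those events as non-serious.
- At the end of the 12 weeks the outcomes assessor asks participants about SAEs (12.2), and all SAEs within the 12 weeks are to be recorded (13.3).
- The REC receives only SAEs that are both related and unexpected (13.3). An expected SAE that is correctly classified would not go to the REC under either reading.

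The net loss is therefore 24-hour notification of the sponsor and the form-based assessment by the chief and local investigators.

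**The case against.** The strongest reply is that 13.4 is a deliberate, specific exception to the general rule in 13.3, and that a specific rule prevails over a general one. Taken with 13.3 alone, that reading is possible, and the fault would then be a missing cross-reference. It does not resolve the conflict with 12.2, which defines expected events as non-serious and so leaves the exception nothing to apply to.

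A second reply is that the events stay visible through the CRF flag, the TMG review and the TSC reports. That is correct, and it limits the consequence. A reader might infer that causality is not collected for these events, or that the safety conclusion would understate related serious harm. The protocol supports neither. The causality duty in 13.3 is not expressly waived, the TMG has a relatedness review, and the events are still recorded and reported by a slower route. For the same reason, expressing a missed event as a share of the 42 participants has no basis: the text does not produce a missed event.

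A third reply concerns breadth. A reader might count several of the seven listed items as potentially serious. The list qualifies pain exacerbation as temporary and flare as a perception, and whether either could become serious is a clinical judgement that the protocol does not make. Only trips, slips and falls plainly extends to serious injury, so the point rests on that item.

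Finally, the lack of a time limit should not be overstated. Section 13.4 does ask for prompt entry, and section 21 leaves data handling to a Data Management Plan that is not at hand. What can be said is that this document sets no hour limit for the CRF route.

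**Conclusion.** The contradiction is real and should be corrected. As written, a serious fall during the circuit is subject to incompatible instructions in 12.2, 13.3 and 13.4. Following 13.4 removes 24-hour sponsor notification, and it removes the form on which relatedness and expectedness are judged without providing a field in its place.

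The size is that of a reporting rule, not of an estimate. No result in the protocol changes, and no expected number of such events is given. Section 13.3 anticipates no intervention-related SAEs, so few cases should arise. REC reporting of correctly classified expected SAEs is unaffected.

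The conclusion assumes that the field list in 13.4 is complete as stated, and that no other study document, such as the Data Management Plan, restores a time limit or a causality item.

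**What to change.** Reconcile sections 12.2, 13.3 and 13.4 so that a site has one instruction for each event. The protocol's own definition in 12.2 gives the simplest way:

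- In 13.4, confine the exemption from the SAE form to listed events that meet none of the seriousness criteria in 13.2.
- State in 13.3 and 13.4 that any event meeting a 13.2 criterion follows the SAE-form, 24-hour and causality route, whether or not its type is listed.
- State that expectedness, as judged by the chief and local investigators, affects only onward reporting to the REC.
- Add a causality field, using the four categories in 13.3, to the expected-event page of the CRF.

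The cost is a change of protocol wording, one CRF field and a few additional SAE forms. Sample size, visits and analysis are unaffected.

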14.1 Supervised intervention sessions

Supervised intervention sessions will be delivered by a physiotherapist or podiatrist to guide participants on how to undertake a home-based gait rehabilitation programme. The delivery of intervention sessions will be pragmatic and flexible according to individual needs and preferences regarding additional attendances. Participants will be required to attend at least 2 face-to-face supervised intervention sessions and up to a maximum of 6 over a 12-week period. Where participants are unable to attend further supervised sessions after the first 2, telephone-based sessions will be provided as required within office hours to maintain contact, promote adherence to the home programme, and/or to provide specific advice regarding progression. The content of all contacts will be audio recorded and recorded on an intervention checklist by the therapists.

To address the physiological principles of overload and specificity, the gait rehabilitation programme will involve a 'gait circuit' comprised of an adapted set of task-specific, weightbearing, functional walking exercises previously employed in RA to target the main muscle groups used during walking [93,94]. Participants will be assessed by the clinician in order to determine baseline functional ability (i.e. can the participant complete each task?). The rationale for gait rehabilitation will be explained and gait circuit tasks will then be demonstrated by the clinician prior to an assessment of participants' competency in undertaking gait circuit tasks. Gait circuit starting levels (dose) and a plan for progression will be established. A reduced circuit will be prescribed for those unable to complete specific tasks due to specific disease -related impairments. Participants will be instructed to complete the gait circuit at home in addition to their usual activities.

The 6-task gait circuit requires minimal set-up and space (at least 3x1 metre unobstructed floor space with two chairs and 4 evenly-spaced markers i.e. small household items such as socks) and uses bodyweight resistance only and which does not require any specialist equipment. A home-based session comprising 3 sets of the full 6-task circuit including a 2 minute warm-up (marching on the spot), 1 minute intervals of task completion and 30 second between-task rest periods would take 28.5 minutes to complete. Progression will be advised at the discretion of the clinician and controlled in 4 ways: - 1) by increasing the number of gait circuit sessions, from 3 up to 5 times per week; 2) participants will be advised to monitor and progress intensity of task completion (by increasing speed) using a modified version of the Borg Rating of Perceived Exertion (RPE) scale (range 6-20) to maintain an RPE from 13 up to 17 (equivalent to 50-80% maximal exertion) [93,94]. Whilst the Borg RPE scale was originally developed to measure exertion of the aerobic system, our co-applicant (LB) has Version Date: 11th Feb 2018

used this scale to guide participants' exercise exertion with success in a trial of upper limb training in RA [94]. This method of self-regulation of exercise exertion is beneficial as perceived rates of exertion are unique to each individual. Participants will be advised to complete tasks in a controlled and coordinated manner; 3) participants will be advised to complete more sets from 3 up to a maximum of 6 and; 4) participants will be advised to increase the duration of each task from 1 minute up to 1 minute and 15 seconds. Participants will be instructed to aim for approximately 10 repetitions within 1 minute and 12 repetitions in 1 minute and 15 seconds for each task (with the exception of task number 2; the heel-to-toe walk, which should be completed 5-6 times) [51]. Should participants successfully undertake a full gait circuit session at the upper limit of progression, they would complete 225 minutes of gait circuit tasks per week in addition to their usual activities.

14.2 Support materials

Support for set up and completion of the gait circuit at home will be provided. Participants will be provided with a high quality illustrated educational booklet, an adherence diary and a DVD including educational material and step-by-step demonstrations of gait circuit home setup and task completion. A secure trial website allowing online access to the DVD content will also be set-up so that those wishing to use smart phones, smart televisions, tablets, and/or personal computers to access support materials via the internet may do so. Home support materials including the DVD and web support will be developed (via patient and public involvement activities) and evaluated as part of the feasibility study before being revised as required for the pilot trial and main trial phases.

14.3 Psychological/behavioural component

In order to address maintenance of progress and prevent reversibility, intervention sessions with the clinician will include an embedded psychological component. This is to address the barriers of adherence to exercise/physical activity based interventions commonly experienced by people with RA such as fear avoidance of activity and poor exercise self-efficacy [17,21-23]. The theory of planned behaviour is recommended for behavioural change interventions in RA [95]. This model places emphasis on individuals' perceived ability to perform a given behaviour and their attitudes to initiate behavioural change [96]. The psychological elements of our intervention are based upon motivational interviewing (MI), which will be enhanced through development of implementation intentions to overcome barriers and facilitate translation of intentions into action [97].

The gait rehabilitation intervention is underpinned by the theory of planned behaviour (TPB) [98,99]. This has been widely used in health psychology to examine behavioural intentions, perceived behavioural control and subjective norms as precursors of actual behaviour. MI is a collaborative, goal oriented style of communication where particular attention is paid to the language of change [100]. It has 4 fundamental processes: engaging, guiding, evoking, and planning and is designed to strengthen personal motivation for, and commitment to, a specific goal by eliciting and exploring a person's own reason for change within an atmosphere of acceptance and compassion. Training in this empathetic and non-Version Date: 11th Feb 2018 Version Number: 1.2

judgemental approach to communication around health behaviour change is suitable for non-specialist health professionals and can therefore be included in the gait rehabilitation programme.

Clinicians will receive training on how to deliver the intervention over two full days. This training will also include practice of important elements of the study including; the recording of consultations and the recording of intervention delivery, starting dose and progression plan recorded on a checklist for fidelity assessment purposes.

15. Statistical analysis plan

Calculation of meaningful levels of change: A two-step iterative approach will be adopted for the selection of the most suitable primary outcome measure for the main trial. To determine the minimal clinical important difference (MCID) for each outcome measure, participant's perceptions of the overall treatment effect will be recorded at 12 week follow-up using a 7point global rating of change scale (defined as change in walking ability) as a patient-rated anchor [101,102]: "Overall how has your walking ability changed since the start of the study?", with a 7-point Likert scale response ("Very much worse", "Much worse", "A bit worse", "No change", "A bit better", "Much better", "Very much better"). In the absence of a gold reference standard for measurement of gait ability in early RA, the first iteration will be to evaluate the longitudinal validity of the primary outcome measure candidates relative to the global rating of change scale. Linear associations of change scores will be determined through correlation statistics between candidate outcome measures and the anchor. Candidate outcome measures will be excluded at the first iteration if they do not achieve the minimum threshold of association ($r \ge 0.65$) with the anchor [101,103]. The minimal important difference for each remaining measure, will be calculated as the mean change score in participants who according to the anchor, improved, minus the mean change score in participants who did not improve or whose symptoms worsened [101,103,105].

Calculation of responsiveness: Responsiveness of the primary outcome candidates to intervention from baseline to 12-week follow-up will be evaluated using four different effect size statistics: the paired t-test, Cohen's d, standardised response mean (SRM) and the Guyatt index (GI) [103-108]. To aid interpretation of the effect size statistics, the following benchmarks will be used: negligible (<0.15), small (\geq 0.15 and <0.40), medium (\geq 0.40 and <0.75), large (\geq 0.76 and <1.10), very large (\geq 1.10 and <1.45) and huge effect size s (>1.45) [104]. The larger the effect size, the more responsive the outcome measure.

Selection of primary outcome for the future randomised trial: For the second iteration, results of the analyses of the primary outcome candidates from the feasibility phase will be compiled in a report which will be presented to the both the TMG and the TSC who will be tasked with recommending which outcome should be taken forward to the main RCT. The TMG will be asked to consider the relative simplicity of the candidate outcome measures (to reduce participant burden), the strength of correlations with the anchor, and responsiveness.

16. Analysis of process outcomes

Remaining analyses will focus on process measures. Analyses will include the following aspects:-

- Acceptability of the intervention will be evaluated using: 3-item acceptability questionnaire and analysed using descriptive statistics and thematic analysis of qualitative data (from participants and clinicians).
- Treatment adherence will be evaluated using: the Exercise Adherence Rating Scale (EARS) and will be summarised using descriptive statistics and thematic analysis of qualitative data (obtained from participants and clinicians).
- Safety of the intervention will be determined by analysis of all reported adverse events and thematic analysis of qualitative data from participants and clinicians.
- Intervention fidelity data will be gathered from participants and trial intervention clinicians and analysed as follows:-

i) deviations from intervention protocols will be recorded using intervention checklists and will be analysed using descriptive statistics.

ii) thematic analysis of qualitative data obtained from clinicians.

iii) audio samples of clinician-participant consultations will be evaluated objectively by independent assessors using an intervention fidelity checklist and the motivational interviewing treatment integrity scale.

For deeper explorations of intervention acceptability, adherence and safety the interview data will be transcribed verbatim. Thematic analysis will be undertaken using a thematic network approach whereby basic themes (lowest order premises) will be grouped together to summarise more abstract principles (organising themes) and global themes which wholly encapsulate the phenomena [109].

17. Software for statistical analysis

Statistical analyses will be carried out using standard statistical software, such as SAS or R.

18. Sample size

For the purposes of evaluating measurement properties of primary outcome candidates, we have selected a minimum magnitude of association (correlation coefficient) between the selected anchor and outcome measures of r=0.65 [101,102]. With a feasibility study sample size of at least n=42, we can detect a correlation \geq 0.65 at 5% significance with 80% power, accounting for 20% attrition.

19. Management and delivery

The Robertson Centre for Biostatistics which is part of the Glasgow Clinical Trials Unit and a fully UKCRC-registered Clinical Trials Unit, will manage and analyse data. All statistical analyses will be conducted according to the pre-specified Statistical Analysis Plan.

20. Study closure / definition of end of study

The study will end when the TSC agrees that one or more of the following situations applies:

• Last participant, last study visit (including qualitative interviews);

OR

i. The planned sample size for each aspect of the study (repeated measures plus embedded qualitative work) has been achieved;

- ii. New information makes it inappropriate to continue to deliver the study intervention;
- iii. Recruitment is so poor that completion of the study cannot reasonably be anticipated.

21. Case report forms

A paper-based case report form (CRF) will be used to collect study data. The CRF will be developed by the study Data Centre at the Robertson Centre for Biostatistics, University of Glasgow. Site-specific personnel will complete the CRF for each participant and will subsequently securely mail completed CRFs to the Data Centre at the Robertson Centre for Biostatistics. Paper-based CRFs will be anonymised and will not include any identifiable information. Study personnel at the Data Centre will enter CRF data into an eCRF for analysis. Access to the eCRF will be restricted, with only authorised data centre personnel able to make entries or amendments to participants' data. It is the investigator's responsibility to ensure completion and to review and approve data captured in the CRF.

All data handling procedures will be detailed in a Study Specific Data Management Plan. Data will be validated at the point of entry into the eCRF and at regular intervals during the study. Data discrepancies will be flagged to the study site and any data changes will be recorded in order to maintain a complete audit trail (reason for change, date change made, who made change).

22. Record retention

To enable evaluations and/or audit from regulatory authorities, the investigator agrees to keep records, including the identity of all participating subjects (sufficient information to link

Version Date: 11th Feb 2018

record), all original signed informed consent forms, serious adverse event forms, source documents, detailed records of treatment disposition in accordance with ICH GCP, local regulations, or as specified in the Clinical Study Agreement, whichever is longer. Data will be retained at the Data Centre for a minimum of 5 years.

23. Study management

Sponsorship: Glasgow Caledonian University will act as the sole sponsor for the trial.

Chief investigator: The CI has overall responsibility for the scientific quality, delivery and conduct of the study and will provide senior support to the GCU PI.

Principal investigator: The PI has responsibility for the scientific quality, delivery and conduct of the study at their site.

Glasgow CTU: The study will be supported by Glasgow CTU (lead). All trial procedures will adhere to respective CTU SOPs and support will be provided by the Project Manager based in Glasgow. The Glasgow CTU will provide a trial coordinator who will be supported by the Project Manager. The Project Manager will work closely with and will support study coordinators based at Keele University and KCL, for local site recruitment, setup and liaison. The CI will be responsible for overall delivery to target and to budget of the study, with support of the Project Manager, coordinators and the TMG.

24. Routine management of study: trial management group

The study will be co-ordinated from the Glasgow Clinical Trials Unit by the Trial Management Group. A TMG will be formed consisting of those individuals responsible for the day to day management of the study such as the CI, the PI, the project manager, lead coordinator, local study regional coordinators, representatives from each participating academic institute, data centre representatives, and the principal investigators from each site. Face-to-face meetings will be held at the beginning of the feasibility study. Regular meetings at defined intervals will be held by conference call. The role of the group is to monitor all aspects of the conduct and progress of the study, ensure that the protocol is adhered to and take appropriate action to safeguard participants and the quality of the study itself.

25. Expertise in the team

Our team is internationally recognised for RA gait and disease-related foot and ankle pain research with a portfolio of studies previously funded from MRC, Arthritis Research UK (ARUK), and EU FP7. The team is led by [name] (Professor in Musculoskeletal Health), with support from [name] (Professor of Rehabilitation) at GCU, as well as [name] (NIHR Research Professor) at Keele, [name] (Professor of Rehabilitation) at King's College London, and [name] (Professor of

Version Date: 11th Feb 2018

Experimental Medicine, Director of Research Institute) at the University of Glasgow. The study requires considerable knowledge and understanding of the impact of the RA disease process and associated symptomology on lower limb biomechanics, gait and management strategies delivered by the multidisciplinary rheumatology teams including physiotherapy and podiatry. The team have extensive expertise in the clinical care and assessment of RA patients with foot and lower limb problems and have delivered clinical services in previous trials. We have published extensively on the impact of RA and disease-related foot problems on gait, risk factors for walking disability, interventions for foot pain, development of disease, foot-specific outcome measures, recommendations for early intervention, systematic reviews of interventions, functional outcome measurement and clinical guidelines for the management of foot problems in RA.

26. Protocol amendments

Any change in the study protocol will require an amendment. Any proposed protocol amendments will be initiated by the CI following discussion with the TSC and any required amendment forms will be submitted to the regulatory authority, REC and sponsor.

The CI and TSC will liaise with the study sponsor to determine whether an amendment is non-substantial or substantial. All amended versions of the protocol will be signed by the CI and sponsor representative.

Before the amended protocol can be implemented, favourable opinion/approval will be sought from the original reviewing REC and Research and Development (R&D) office(s).

27. Ethical conduct of the study

The study will be carried out in accordance with the World Medical Association Declaration of Helsinki (1964) and its revisions (Tokyo [1975], Venice [1983], Hong Kong [1989], South Africa [1996], Edinburgh [2000], Seoul [2008] and Fortaleza [2013]).

Favourable ethical opinion will be sought from West of Scotland Research Ethics Service before participants are entered into this study. The CI will be responsible for updating the REC of any new information related to the study.

28. Informed consent

Written informed consent will be obtained from each study participant. The research nurse or investigator will explain the exact nature of the study in writing by provision of the participant information sheet and verbally. This will include the known side-effects that may be experienced and the risks of participating in this study. Study participants will be informed that they are free to withdraw their consent from the study or study treatment at any time.

29. Insurance and indemnity

The GREAT-FS study is sponsored by Glasgow Caledonian University. The sponsor will be liable for negligent harm caused by the design of the study. Glasgow Caledonian University will provide legal liability cover for their employed staff. NHS indemnity will apply for all patients treated within NHS sites.

The NHS has a duty of care to patients treated, whether or not the patient is taking part in a study involving exposure to new interventions and the NHS remains liable for clinical negligence and other negligent harm to patients under its duty of care.

30. Funding

This study is funded by the National Institute of Health Research (NIHR) Health Technology Assessment (HTA) scheme (grant reference 15/165/04).

31. Timescales

October 2017 – December 2017 – develop and finalise the protocol for the feasibility study, first trial steering committee to finalise the protocol, finalise recruitment procedures and documentation for ethics application.

November 2017 – February 2018 – submit research ethics application and subsequently R&D applications, deliver intervention and protocol training to intervention delivery staff, setup procedures and site initiation visits.

January 2018 – July 2018 – recruitment of study participants, delivery of intervention over 12 weeks, commence follow ups following completion of 12 week intervention period, data entry.

July 2018 – September 2018 – completion of study follow-ups, completion of qualitative data collection, data entry and analysis.

September 2018 – December 2018 – complete data analysis, write-up and finalise gait rehabilitation intervention for internal pilot trial. A separate protocol will be developed and submitted for approvals for the internal pilot and main trial.

